6.2 Safety evaluation (Not applicable)

6.3 Genetics as a co-variate

6.3.1 Calculation or derivation of genetic variables

Not applicable.

6.4 Statistical methods and determination of sample size

6.4.1 Statistical evaluation

Statistical analysis will be carried out by Quality Data Services (QDS), King of Prussia under the direction of Biostatistics at AstraZeneca, Wilmington, using SAS (version 8). Graphics required for presentation in the text portion of the Clinical Study Report (CSR) will be done using SAS or Sigmaplot 2000. Other graphics intended for supplemental figures and individual time plots will be done using SAS.

6.4.2 Description of variables in relation to hypotheses

6.4.2.1 Primary objective

In order to assess the absolute bioavailability of AZD6140 following oral and intravenous administration, the dose-normalized AUC values for the two formulations of AZD6140 will be computed.

6.4.2.2 Secondary objectives

Characterization of the pharmacokinetics of AZD6140 following oral and intravenous administration of AZD6140 will be based on single dose C_{max} , t_{max} , $AUC_{(0-t)}$, AUC, $t_{1/2}$, and CL/F of AZD6140.

Characterization of the pharmacokinetics of AR-C124910XX following oral and intravenous administration of AZD6140 will be based on single dose C_{max} , t_{max} , $AUC_{(0-t)}$, AUC, $t_{1/2}$ of AR-C124910XX; and AR-C124910XX:AZD6140 C_{max} and AUC ratios.

Characterization of the pharmacokinetics of AZD6140 and AR-C124910XX after oral administration of AZD6140 will be based on single dose AUMC, MRT oral and MAT and CL/F for AZD6140.

Characterization of the pharmacokinetics of AZD6140 and AR-C124910XX after intravenous administration of AZD6140 will be based on single dose AUMC, MRT (IV) and CL, V_{ss} , and V_z for AZD6140. The safety and tolerability of AZD6140 will be examined by collection of adverse events, vital signs, and clinical laboratories.

The examination of the safety and tolerability of AZD6140 will be conducted based on AE, clinical lab, vital sign and ECG data.

6.4.3 Description of analysis sets

6.4.3.1 Pharmacokinetics analysis set

The pharmacokinetics analysis set will include all volunteers who provide sufficient data to estimate the pharmacokinetic parameters of AZD6140 and AR-C124910XX following administration of each formulation involved in the contrast of interest with no deviations, which would interfere with the absorption, distribution, metabolism, or excretion of AZD6140.

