1. INTRODUCTION

1.1 Background

Adenosine diphosphate (ADP) is an important mediator of platelet activation and aggregation through its binding to at least 2 distinct subtypes of purinoceptor, designated P2Y₁ and P2Y₁₂, found on platelets. Two ADP receptor antagonists, thienopyridine prodrugs, PLAVIX™ (clopidogrel) and TICLID™ (ticlopidine) have shown clear benefits for the reduction of clinical thrombotic events in patients with atherosclerosis due to their ability to block the P2Y₁₂ receptor. However, this blockade is irreversible and usually incomplete. Therefore, the search continues for agents that can further improve the clinical outcomes of these patients through improved efficacy and/or safety.

AZD6140 is a potent, reversible, selective P2Y₁₂-receptor antagonist (antiplatelet agent) being developed to reduce thromboembolic events in patients with atherosclerosis. It is orally active and does not require metabolic activation, different from clopidogrel, for which only the metabolites are active. Unlike clopidogrel and ticlopidine, which incompletely block the P2Y₁₂-receptor response in humans, pre-clinical studies indicate that AZD6140 can produce reversible and complete inhibition of ADP-induced platelet aggregation *ex vivo* following oral dosing. Additionally, AZD6140 has shown greater and more consistent inhibition of platelet aggregation compared to clopidogrel in both healthy volunteers and patients. It has also demonstrated a faster onset and offset of antiplatelet effect. These properties suggest that AZD6140 may be able to reduce the occurrence of thrombotic events compared to clopidogrel with an acceptable safety profile.

AZD6140 binds to plasma proteins (>99.7%), and is extensively metabolised by CYP3A4/5, with little parent drug excreted unchanged in the urine. AZD6140 has a number of drug–drug interactions of clinical relevance since it is a substrate, inhibitor, and activator of CYP3A4 /5 and a substrate and inhibitor of the P-glycoprotein transporter. Following an oral dose of ¹⁴C-labelled AZD6140 in humans, approximately 27% was excreted in the urine and 57.8% in the faeces. The elimination half-life (t_{1/2}) of the parent compound is approximately 11 hours after single dose administration.

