One of the primary metabolites, AR-C124910XX, is considered equipotent to the parent drug in the *in vitro* studies. The time course of the pharmacologically active metabolite approximately parallels AZD6140; the area under the plasma concentration curve (AUC) and maximum plasma drug concentration after single dose administration (C_{max}) of AR-C124910XX is typically 30 to 40% of the corresponding parameters for AZD6140.

Plavix™ (Clopidogrel bisulfate) is a registered trademark of Sanofi Aventis and distributed by Bristol-Myers Squibb/Sanofi Pharmaceuticals Partnership, NY, NY.

TICLID™ (ticlopidine) is a registered trademark of Roche Pharmaceutical, Inc, Nutley, NJ.

Adverse events (AEs) reported with a frequency of at least 2% in Phase 1 studies with at least 3 days of AZD6140 dosing include: headache, somnolence, dizziness, epistaxis, nausea, abdominal pain, back pain, dyspnoea, ecchymosis, lethargy, pharyngolaryngeal pain, blurred vision, postural dizziness, pollakiuria (frequent urination), and increased tendency to bruise. Two serious adverse events (SAE) occurred during the Phase 1 program; an occurrence of chronic mediastinitis not considered by the investigator to be related to study drug, and an episode of sinus pause (high grade atrioventricular block and ventricular escape rhythm associated with syncope) in a volunteer who received a single 1260 mg dose of AZD6140. The volunteer recovered without sequelae, and the event was considered to be medically important and related to study drug.

Refer to the Investigator Brochure for further details on AZD6140 exposure, pharmacokinetic, and safety findings. These data support the further development of AZD6140 as an oral antiplatelet agent, which may be able to prevent more thrombotic events than clopidogrel by sustaining higher levels of P2Y₁₂ receptor blockade with an acceptable safety profile.

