2.2 Secondary objective(s)

The secondary objectives of the study are:

- To characterize the pharmacokinetics of AZD6140 following oral and intravenous administration of AZD6140.
- To characterize the pharmacokinetics of AR-C124910XX following oral and intravenous administration of AZD6140.

- To examine the safety and tolerability of AZD6140.

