4.2.1 AZD6140 and metabolite

4.2.1.1 Determination of drug concentration in biological samples

Samples for measurement of drug concentration of AZD6140 and its active metabolite, AR-C124910XX in plasma will be analyzed by York Bioanalytical Solutions, Upper Poppleton, York, UK on behalf of Development Drug Metabolism and Pharmacokinetics (DMPK) & Bioanalysis, Mölndal, AstraZeneca using fully validated bioanalytical methods. The lower limit of quantification (LLOQ) will be 5 and 2.5ng/mL, respectively. Details of the methods used will be provided in the clinical study report (CSR). Samples will be disposed of after the CSR is finalized.

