6.4.4 Methods of statistical analyses

The aim of this analysis is to determine the absolute bioavailability of AZD6140 following oral and intravenous administration.

The primary variables will be AUC (oral), AUC (IV), (Dose (IV) and Dose(oral) which are used in the calculation of Primary Endpoint F (Absolute bioavailability), where $F = (AUC(oral)/AUC(IV)) * (Dose(IV)/Dose(oral))$.

The primary contrast will be AZD6140(90 mg oral dose) vs. AZD6140(15 mg intravenous infusion).

Unless otherwise specified, descriptive statistics will include N, mean, standard deviation, minimum, median, and maximum.

A comprehensive statistical analysis plan will be prepared and finalized prior to database lock.

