6.4.4.1 Pharmacokinetics

Only data from volunteers in the PK analysis set will be summarized and formally analyzed. All PK and plasma concentration data will be listed. Any data excluded from the analysis will be flagged accordingly.

The absolute bioavailability (F), where $F = (AUC(oral)/Dose(oral))/(AUC(IV)/Dose(IV))$, of AZD6140 following oral and intravenous administration will be analyzed as follows: Dose-normalized AUC values for the two formulations of AZD6140 will logarithmically transformed. An ANOVA model will then be fit using these log-scale values. The effect of formulation will be the primary contrast [$\log(AUC(oral)/Dose(oral)) - \log(AUC(IV)/Dose(IV))$]. The effect of formulation will be estimated using the $1s_{mean}$ and its 95% confidence interval. The $1s_{mean}$ and 95% confidence interval will then be exponentiated in order to estimate the absolute bioavailability. The $1s_{means}$ and 95% confidence intervals will also be calculated and exponentiated for each treatment formulation

PK parameters and plasma concentration data for each moiety (AZD6140, AR-C124910XX) will be summarized using descriptive statistics by AZD6140 formulation. Descriptive statistics will also include geometric mean and CV for all parameters except t_{max} , which will be summarized using only N, minimum, median and maximum. Geometric mean and individual plasma concentration-time profiles will be presented by AZD6140 formulation. AUC and C_{max} for each moiety will also be presented graphically as a function of AZD6140 formulation.

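### The PK analysis set makes entry to the primary analysis of F depend on metabolite parameters that F does not use; how often this would matter is unknown and it is cheap to fix.

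*Protocol*

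**What the plan says.** Section 6.4.3.1 gives a single PK analysis set. Members must provide "sufficient data to estimate the pharmacokinetic parameters of AZD6140 and AR-C124910XX following administration of each formulation involved in the contrast of interest" and have no deviation that would interfere with the disposition of AZD6140. Section 6.4.4.1 then states: "Only data from volunteers in the PK analysis set will be summarized and formally analyzed". The analysis of F follows in that same section. All PK and concentration data are to be listed, and exclusions flagged.

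For the primary objective, section 6.4.2.1 says that "the dose-normalized AUC values for the two formulations of AZD6140 will be computed". Section 6.4.4 defines F from the two AUCs and the two doses and adds: "The primary contrast will be AZD6140(90 mg oral dose) vs. AZD6140(15 mg intravenous infusion)". The metabolite appears only in a secondary objective (section 2.2): "To characterize the pharmacokinetics of AR-C124910XX following oral and intravenous administration of AZD6140". No parent-only or analyte-specific set is defined.

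**The concern.** The membership rule joins the two analytes with a plain conjunction, while the primary endpoint needs only one of them. A complete pair of AZD6140 profiles could therefore be set aside for a reason that has no bearing on F.

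At stake is primary information in a small study. About 12 volunteers are randomised to secure 10 evaluable (sections 3.1 and 6.4.5), so the margin is two. An exclusion that depends on metabolite exposure might also be related to first-pass loss, in which case the volunteers who remain would not be a neutral subset for estimating F.

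A smaller matter has the same source. The set requires data after each formulation in the contrast, so a volunteer who completes only the infusion period appears to drop out of the summaries of CL, Vss and Vz, which need no oral data.

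**Working it through.** The protocol states that no formal sample size calculation was done, so there is no planned precision to reproduce. The check has three parts.

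**1. What the rule does.** Setting the sections side by side:
- Contrast of interest: 90 mg oral against 15 mg intravenous (6.4.4), so both routes are required.
- Analytes required for membership: parent and metabolite (6.4.3.1).
- Analyte required for F: parent only (6.4.2.1, 6.4.4, 6.4.4.1).
- Analysis allowed outside the set: none (6.4.4.1).

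The reference to the contrast of interest narrows membership by formulation, not by analyte. The metabolite condition therefore applies to F.

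**2. Whether the metabolite can fail where the parent does not.** Inputs: "The lower limit of quantification (LLOQ) will be 5 and 2.5ng/mL, respectively" for parent and metabolite (4.2.1.1); metabolite AUC and Cmax "is typically 30 to 40% of the corresponding parameters for AZD6140" (1.1); and a half-life that "of the parent compound is approximately 11 hours after single dose administration" (1.1). Take headroom as concentration divided by LLOQ.
- Metabolite headroom relative to parent = r / (2.5/5), where r is the metabolite:parent ratio.
- r = 0.30: 0.30/0.5 = 0.60. r = 0.40: 0.40/0.5 = 0.80.
- If the metabolite declines in parallel at the 11 h half-life, it reaches its LLOQ earlier by 11 × log2(1/0.60) = 8.1 h or 11 × log2(1/0.80) = 3.5 h.
- The extrapolated share of AUC is about LLOQ/(λz × AUC). With a common λz, the metabolite share relative to the parent's is 0.5/r, which is 1.67 at r = 0.30 and 1.25 at r = 0.40.

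The metabolite is the harder analyte to characterise, by a modest factor. The 30 to 40% ratio is stated generally and not for the intravenous route.

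**3. What a loss would cost.** The half-width of the log-scale 95% interval is proportional to t(0.975, n−2)/√n. The n−2 degrees of freedom assume a standard two-period crossover ANOVA; the protocol does not list the model terms.

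| n | t(0.975, n−2) | t/√n | relative to n = 10 |
|---|---|---|---|
| 12 | 2.228 | 0.643 | 0.88 |
| 10 | 2.306 | 0.729 | 1.00 |
| 8 | 2.447 | 0.865 | 1.19 |
| 7 | 2.571 | 0.972 | 1.33 |

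At an assumed within-subject CV of 30%, the interval factor exp(t × s_w × √(2/n)), with s_w = √ln(1 + CV²), is ×/÷1.35 at n = 10 and ×/÷1.43 at n = 8.

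Suppose metabolite parameters were inestimable in an assumed 5%, 10% or 20% of volunteers, with no other losses. The binomial probability that at least 10 of 12 remain evaluable would be 0.98, 0.89 or 0.56. Under a parent-based rule such failures would not affect the primary set at all.

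**The case against.** The best defence is that the wording rarely bites. Section 6.4.3.1 asks only for enough data to estimate, and section 6.1.1 extrapolates AUC to infinity with no limit on the extrapolated share. A heavily extrapolated metabolite AUC is still an estimate. Sampling runs to 72 h on both routes, and section 1.1 says the metabolite roughly parallels the parent. The margin of two absorbs the first losses, and volunteers who withdraw may be replaced at the sponsor's discretion (3.3.5.2, 3.4.3). What counts as sufficient data can reasonably be settled in the SAP. All of this stands as to frequency and size. It does not remove the metabolite condition, which the protocol states rather than leaves open. A parent-only primary set in the SAP would depart from 6.4.3.1.

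A reader might infer more than the documents support:
- **That the metabolite profile after the infusion is the likeliest to fail.** No intravenous metabolite ratio is given, and infused drug is still metabolised systemically. The intravenous:oral parent AUC ratio is (15/90)/F = 1/(6F), and F is unknown (1.2); at F = 1/6 the two exposures are equal.
- **That large extrapolated shares will exclude volunteers.** Absolute shares need an intravenous AUC that the protocol does not give, and no cut-off turns a share into an exclusion.
- **That F will be biased.** A shift of about 4% can be produced (0.275 SD × 0.5 × 0.3 = 0.041). It needs the two lowest metabolite formers of 12 to be lost, a correlation of 0.5 with log F and an SD of log F of 0.3, all of them assumed. It is also small beside the interval in the working.

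**Conclusion.** The defect is real but limited. As written, sections 6.4.3.1 and 6.4.4.1 remove a volunteer with an estimable AZD6140 AUC after both routes from the analysis of F when AR-C124910XX parameters cannot be estimated after either route. The documented ratio and LLOQs show that this is possible. They do not show how often it would occur, and it is probably infrequent.

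With no other losses, two such exclusions still leave the intended 10. Going from 10 to 8 would widen the log-scale interval by 19%, but nothing in the protocol indicates that this many volunteers would be lost. Any bias is conjectural. The study estimates F without a test or acceptance limit, so no decision threshold is at risk. This is a minor to moderate point, worth correcting because the correction costs almost nothing and decides who enters the primary analysis.

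**What to change.** Amend sections 6.4.3.1 and 6.4.4.1 before concentration data are seen:
- **Primary PK set:** volunteers with an estimable AZD6140 AUC after both treatments and no deviation affecting AZD6140 disposition, regardless of whether metabolite parameters can be estimated.
- **Metabolite set:** defined separately, for AR-C124910XX parameters and the metabolite:parent ratios.
- **Single-route descriptive parameters:** summarised in all volunteers with an estimable value for that route.

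The cost is a few sentences, with no added volunteers or samples. The one drawback is that N may differ between tables, so each table needs a footnote giving its N and the reason for any exclusion.

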1.2 Rationale

The purpose of this study is to help complete the pharmacokinetic characterization of AZD6140. AZD6140 is extensively metabolized by CYP3A and other enzymes, and is a substrate of P-glycoprotein, an efflux transporter located in the gastrointestinal tract and the liver. The absolute bioavailability of orally administered AZD6140 (an estimate of the fraction of the dose that reaches the systemic circulation intact or escapes the “first pass effect”) is not currently known. The minimal extent of absorption is at least 27% based on the urinary recovery of total radioactivity following oral administration of a ¹⁴C-AZD6140 dose. Use of the intravenous dose in this study will allow the estimation of the absolute bioavailability (F) following oral dosing, the total body or systemic clearance (CL) and the volume of distribution (V_{ss}) of AZD6140.

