3.4.3 Method of assigning volunteers to treatment groups

Written informed consent will be obtained before enrolment and the volunteers identified with an enrolment number starting with E0001001. Volunteers fulfilling the eligibility criteria will be assigned volunteer numbers starting with 101 prior to dosing.

Volunteers will be assigned volunteer numbers strictly sequentially as volunteers are eligible for dosing. If a volunteer discontinues from the study the volunteer number will not be re-used and the volunteer will not be allowed to re-enter the study. If a volunteer discontinues from the study that volunteer may be replaced at the discretion of the sponsor.

QDS will generate the treatment randomisation code using its internal SAS v. 8.2-based randomisation application. QDS will complete the necessary AstraZeneca Global Randomisation (GRand) request form and transfer the form and treatment randomisation to AstraZeneca for importation into the GRand system. QDS will retain the original treatment

randomisation code. QDS will generate additional randomisation treatment assignments for replacement volunteers if necessary and follow the process as previously described.

All study drug will be dosed open label. Before study drug administration on Day 1 of Period 1, healthy volunteers who are eligible to continue the study will be randomised to one of two treatment sequences (AB or BA), in a balanced fashion, strictly sequentially. If the healthy volunteer should be incorrectly randomised, randomisation should continue with no attempt to correct the error. If a healthy volunteer discontinues from the study, the randomisation number will not be re-used, and the healthy volunteer will not be allowed to re-enter the study. Volunteers who discontinue prematurely will not be replaced unless it appears that sufficient volunteers will not complete the study. The randomisation of replacement volunteers will be at the discretion of the sponsor.

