6. PHARMACOKINETIC, PHARMACODYNAMIC, SAFETY, GENETIC AND STATISTICAL METHODOLOGY

6.1 Pharmacokinetic / pharmacodynamic evaluation

6.1.1 Calculation or derivation of pharmacokinetic variables

The pharmacokinetic analyses will be performed by Clinical Pharmacokinetics, Clinical Pharmacology, AstraZeneca, Wilmington, DE USA.

Plasma concentrations of AZD6140 and its metabolite ARC124910XX will be listed and depicted graphically as a function of time after single oral and intravenous doses.

PK parameters- 1) C_{max} , t_{max} , $t_{1/2}$, $AUC_{(0-t)}$ and AUC for AZD6140 and AR-C124910XX after intravenous and oral doses; 2) $AUMC$, MRT (IV) for AZD6140 and AR-C124910XX; and CL , V_{ss} , and V_z for AZD6140 after intravenous dosing and 3) $AUMC$, MRT oral and MAT after oral dosing for AZD6140 and AR-C124910XX, as well as CL/F for AZD6140 after oral dosing; will be estimated using non-compartmental analysis. Metabolite: parent C_{max} and AUC ratios will be calculated following IV and oral dosing. C_{max} will be estimated as the highest measured concentration and t_{max} is the time to maximum concentration after single dose administration. The terminal elimination rate constant (λ_z) will be calculated by log-linear regression of the terminal portion of the plasma concentration-time profile. The terminal elimination half-life ($t_{1/2}$) will be calculated as $0.693/\lambda_z$. AUC and $AUMC$ will be calculated using the linear trapezoidal method up to the last measurable concentration (AUC_{0-t}) and thereafter by extrapolation of the terminal elimination phase to infinity. AZD6140 CL and CL/F will be estimated as the ratio of AZD6140 dose and AUC after intravenous and oral doses, respectively. Mean residence time (MRT) will be calculated as the ratio of $AUMC$ to AUC with a correction for non-instantaneous infusion input following intravenous administration. Mean absorption time (MAT) will be estimated as the difference between MRT oral and MRT IV. Steady state volume of distribution (V_{ss}) will be estimated as the product of CL and MRT iv, and terminal phase volume of distribution, V_z , will be estimated as the ratio of CL to λ_z .

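### The single PK analysis set requires evaluable data after both routes, so a valid one-route profile is listed but left out of descriptive summaries that need only that route (minor)

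*Protocol*

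**What the plan says.** Protocol Section 6.4.3.1 defines one PK analysis set. A volunteer belongs to it if the parameters of parent and metabolite can be estimated "following administration of each formulation involved in the contrast of interest with no deviations, which would interfere with the absorption, distribution, metabolism, or excretion" of the drug. Section 6.4.4 names one comparison: "The primary contrast will be AZD6140(90 mg oral dose) vs. AZD6140(15 mg intravenous infusion"). With no other contrast defined, each formulation means both.

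Section 6.4.4.1 opens with "Only data from volunteers in the PK analysis set will be summarized and formally analyzed". The by-formulation descriptive statistics and the concentration summaries follow under that restriction. The next sentence says "All PK and plasma concentration data will be listed", with excluded data flagged. No second PK set and no exception for single-route summaries is given.

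Section 6.1.1 derives the clearances route by route: "AZD6140 CL and CL/F will be estimated as the ratio of AZD6140 dose and AUC after intravenous and oral doses, respectively". Section 1.2 says the IV dose will allow estimation of F and also of "the total body or systemic clearance (CL) and the volume of distribution (V_{ss}) of AZD6140". Sections 2.2 and 6.4.2.2 make the pharmacokinetics after each route a secondary objective.

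On replacement, Section 3.4.3 states: "Volunteers who discontinue prematurely will not be replaced unless it appears that sufficient volunteers will not complete the study".

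**The concern.** The both-route condition suits a within-volunteer comparison. F needs it, and so does MAT, which is a difference between two routes. CL, Vss, Vz and MRT after IV each come from one IV profile. CL/F and MRT after oral dosing each come from one oral profile, and by-route Cmax, AUC, t1/2 and concentrations likewise need one profile only. A rule built for the primary contrast is therefore applied to secondary summaries that do not use the contrast.

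The case can arise under the protocol's own procedures. Table 1 repeats the eligibility check, pregnancy test and urine alcohol and drug screen on Day -1 of Period 2. Sections 4.4.1.1, 4.4.1.2 and 4.4.1.4 make continuation depend on the results. A volunteer in sequence BA who is stopped there may already have a full 72-hour IV profile. Under the text as written, that profile does not enter the CL or Vss summary because of something unrelated to the infusion.

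At stake is a small amount of information on two quantities that Section 1.2 says the IV dose is there to estimate. Replacing the volunteer, where the sponsor chooses to, does not bring the excluded profile back.

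**Working it through.** **Which parameters need which route (Section 6.1.1)**

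- CL = IV dose / IV AUC: IV only.
- MRT after IV = AUMC / AUC with an infusion correction: IV only.
- Vss = CL × MRT after IV: IV only.
- Vz = CL / λz: IV only.
- CL/F = oral dose / oral AUC: oral only.
- MRT after oral = AUMC / AUC: oral only.
- Cmax, AUC, t1/2 and concentrations by formulation: one profile each.
- MAT = MRT oral − MRT IV: both routes.
- F = (oral AUC / oral dose) / (IV AUC / IV dose): both routes.

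Only the last two need the condition that Section 6.4.3.1 sets for all of them.

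**How many profiles are exposed**

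Section 6.4.5 says that no formal sample size calculation was made, so there is no formula-based figure to reproduce. Section 3.1 randomises about 12 to have at least 10 evaluable. The implied allowance is 2/12 = 17%, and 10 / (1 − 2/12) = 12 is consistent with it. The protocol states no drop-out rate.

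- Ceiling for one route: 2 of 12. This needs both non-evaluable volunteers to have a valid profile for the same route.
- More likely: sequences AB and BA are balanced (Section 3.4.3). If two volunteers leave after Period 1 independently of sequence, the expected number with an IV profile is 2 × 1/2 = 1, and likewise 1 with an oral profile. Each route would then have about 11 profiles instead of 10.
- Floor: 0, if all complete without a relevant deviation.

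**What that is worth in precision (illustration only)**

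Section 6.4.4.1 plans 95% confidence intervals for the formulation contrast and for each formulation's least-squares mean of log dose-normalised AUC. It plans none for CL, Vss, Vz or MRT. The following is a notional one-sample interval for a log-transformed parameter, with half-width t(0.975, n−1) × s / √n:

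- n = 10: 0.715 s.
- n = 11: 0.672 s. 1 − 0.672/0.715 gives 6% narrower.
- n = 12: 0.635 s. 1 − 0.635/0.715 gives 11% narrower.

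The protocol gives no CV, so the CV is an assumption here. With s = √ln(1 + CV²), the limits as multiples of the geometric mean are:

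- CV 20%: 0.868 to 1.152 at n = 10; 0.875 to 1.142 at n = 11; 0.882 to 1.134 at n = 12.
- CV 30%: 0.811 to 1.234; 0.821 to 1.218; 0.830 to 1.205.
- CV 50%: 0.713 to 1.402; 0.728 to 1.373; 0.741 to 1.350.

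The gain is real but modest over this range.

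**The case against.** The strongest case for leaving the text alone has four parts.

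1. A common set is coherent. With the same volunteers in both columns, CL, CL/F and F describe one group, and metabolite-to-parent ratios are compared in the same people. This is a fair reason to prefer it, and the fix gives up some of it. F and MAT, where pairing matters, would keep the paired set.

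2. The condition is worded "following administration of each formulation involved in the contrast of interest", and a by-formulation descriptive table contains no contrast. One could read the both-route rule as applying to the F analysis only. But Section 6.4.4.1 applies the same set to every summary without exception. If the narrower reading was meant, the text should say so.

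3. The statistical analysis plan promised in Section 6.4.4 may set inclusion parameter by parameter. It may, but here the protocol states a rule, so a different rule in that plan would depart from the protocol.

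4. Ten evaluable volunteers is the intended basis, no precision target is missed, and the individual values are still listed. All of this stands. It limits the weight of the point without removing it.

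A reader might also infer that the CL and Vss summaries would be biased because they rest on completers. The documents do not support that: nothing in them links non-completion to clearance or volume. Nor does the protocol say how vomiting after the tablet would be classified, so it cannot be cited as a case in which an unaffected IV profile would be excluded. Being stopped between periods is the case that the text supports.

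**Conclusion.** The point holds as a minor one. Sections 6.4.3.1, 6.4.4 and 6.4.4.1, read together and literally, keep a volunteer with one valid profile out of the descriptive summaries for that route, although those summaries need nothing from the other route. The values remain in the listings.

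A reader might infer that the primary result is weakened or that 17% of the IV data will be thrown away. Neither follows. F is a within-volunteer contrast and properly uses the paired set. Two of 12 is a ceiling for any one route; about one per route is more likely, assuming two departures after Period 1 that are independent of sequence. The 6% and 11% figures correspond to n = 11 and n = 12 against n = 10. They describe a notional interval that the protocol does not plan for CL, Vss, Vz or MRT.

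**What to change.** In Sections 6.4.3.1 and 6.4.4.1:

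- Keep the both-formulation requirement for F, including the model that estimates it, and for MAT.
- For the by-formulation descriptive statistics and concentration summaries, include every volunteer with an evaluable profile for that formulation.
- Judge deviations that could affect absorption, distribution, metabolism or excretion separately for each period.
- Show N for each column.

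This takes about two sentences and needs no extra volunteer or sample. The cost is that N may differ between the oral and IV columns and from the F analysis, so the columns would no longer describe exactly the same people.
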